### 3.0 Inclusion and Exclusion Criteria

Table 1. Inclusion and Exclusion Criteria	
Eligibility Criteria:	Exclusion Criteria:

1. ≥ 18 years of age

2. Self-identify as Black, Hispanic, American Indian, or NLW

3. Clinically significant anxiety and/or depressive symptoms as evinced by a score of 8 or higher on the Overall Anxiety Severity and Impairment Scale (OASIS) and/or Overall Depression Severity and Impairment Scale (ODSIS)

4. Reside in the United States

	

1. Not fluent in English

2. Lifetime or significant cognitive impairment

**FULL PROTOCOL TITLE:** Mobile Health to Monitor Risk for COVID-19 and Improve Mental Health during the Pandemic

5. Willing/able to complete EMAs on study provided or personal smartphone for 6-month study period 6. Willing and able to complete the 3- and 6-month follow-up assessments via Insight™ app and over the phone (i.e., qualitative interview) 7. Score $\geq 4$ on the REALM-SF indicating > 6th grade English literacy level (needed to complete EMAs)	4. Identifying as a race/ethnicity for which the corresponding study cell has been filled
---	---

Participants will be recruited online via social media and internet outlet (e.g. Craigslist, Facebook) advertisements that target residents of the United States. Individuals who click our ads will read the study description and complete a brief study screener in REDCap. Further, we will utilize Qualtrics Panels Recruitment as a method of recruiting new participants. Qualtrics will reach out to individuals who express interest in participating in order to determine eligibility of recruited individuals, Qualtrics will have access to identifiable information to include the following: (1) Full name, (2) Phone number, (3) Phone number (secondary), (4) Email address, (5) Age, (6) Date of birth, (7) Ethnicity, (8) Race, (9) Gender assigned at birth. The Qualtrics survey will also utilize the Overall Anxiety Severity and Impairment Scale and the Overall Depression Severity and Impairment Scale. Additionally, we will be recruiting participants using university and online LISTSERV services. Also, we will be recruiting American Indian participants through BuildClinical. BuildClinical will direct individuals to their own platform where they will receive more information about the study. They will also be able to take our pre-screener survey through BuildClinical and we will be able to download a list of pre-eligible participants. This program will have access to the following information: (1) Full name, (2) Phone number, (3) Phone number (secondary), (4) Email address, (5) Age, (6) Date of birth, (7) Ethnicity, (8) Race, and (9) Gender assigned at birth. BuildClinical will create all recruitment materials for use on their platform once recruitment through BuildClinical is approved by the University of Houston Institutional Review Board. Those who initially meet the study inclusion criteria will complete a phone call with study staff after completing the REDCap screener. During this call, study staff will verify that individuals meet the study inclusion criteria.

The REDCap screener will include assessment of demographics, anxiety (OASIS), depression (ODSIS), and state of current residency. Demographic-Treatment History Questionnaire will assess sex, age, race and ethnicity, occupation, and current monthly income. The OASIS is a 5-item measure that has demonstrated strong psychometric properties to identify those with clinically significant anxiety. The ODSIS is a 5-item measure that has demonstrated strong psychometric properties to identify those with clinically-significant depression. Potentially eligible participants will be asked to upload a picture to confirm their identity (such as a photo ID). If their identification photo information does not fully match (e.g. last name change), the participant can provide a secondary form of identification to confirm their identity. At the phone screener, a trained research assistant will obtain informed consent, confirm the state of residency by requesting participant address and current location, assess literacy, evaluate cognitive impairment using the Six Item Cognitive Impairment Test (6CIT), and assess English literacy. The trained research assistant will also obtain U.S. residency status, date of birth, and social security number. To be in compliance with IRS regulations, the University of Oklahoma must collect residency status for all participants and all payments are required to be reported as outlined in this policy. Further, participant name, tax identification number (SSN or ITIN), address, amount paid and source of funding for the payment will be collected. The full participant payment policy for the Oklahoma University Health Sciences Center can be found here: <https://www.ouhsc.edu/policy/#19931991-section-557---participant-payment-policy>. We would like to stress that U.S. citizens, Permanent Residents, Resident Aliens, and Non-Resident

**FULL PROTOCOL TITLE:** Mobile Health to Monitor Risk for COVID-19 and Improve Mental Health during the Pandemic

Aliens will receive equal compensation for their participation. Per the Oklahoma Taxpayer and Citizen Protection Act of 2007, undocumented immigrants are prohibited from receiving payment, and thus will be excluded from this study. The informed consent procedure will be completed by phone and REDCap (i.e., participants will use REDCap to review the informed consent document along with research staff, REDCap will be used to obtain signatures). The REALM-SF will be employed to assess literacy.

Economically disadvantaged persons will be included in the study as research suggests that a significant portion of BLAI individuals are low income.

None of the following populations will be specifically recruited:

- Adults unable to consent
- Individuals who are not yet adults (infants, children, teenagers)
- Pregnant women
- Prisoners
- Students for whom you have direct access to/influence on grades

## **4.0 Vulnerable Populations**

N/A

## **5.0 Number of Subjects**

**STUDY-WIDE:** Taking failed screeners and participant attrition into account, we expect to consent 1300 participants. We anticipate randomizing a total of 880 participants (N = 880; 220 Black, 220 Hispanic, 220 American Indian, and 220 NLW; Intervention group, n=440, control group, n=440).

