## 1.0 Objectives

1.1 The proposed research is directly relevant to public health because it aims to target health disparities in access to behavioral health care during the COVID-19 pandemic among Black, Hispanic, and American Indian (BLAI) individuals via testing an adaptation of an established, initially validated, low-cost, mobile application ('app') designed to reduce ongoing mental health concerns among BLAI individuals with elevated anxiety and/or depressive symptoms (Easing Anxiety Sensitivity for Everyone [EASE] App). Using a precision medicine approach, EASE targets anxiety sensitivity, a transdiagnostic individual difference factor implicated in the etiology, maintenance, and progression of anxiety and depressive symptoms. EASE includes COVID-19 symptom monitoring, exposure management skills, and psychoeducation on COVID-19-related stress and the impact of stress on susceptibility to infection and disease progression; if successful, this study will provide evidence that the EASE app-based intervention can address the public health concerns of anxiety and depressive symptoms among BLAI during the COVID-19 crisis. **Aim 1.** To compare the effect of EASE with COVID-19 specific elements (n = 420) to a standard-of-care digital intervention with educational material covering stress reduction, and anxiety and depression symptom management and COVID-19 specific elements (n = 420). To evaluate the efficacy of the experimental intervention across each race/ethnic group. **Aim 2.** To identify the therapeutic mechanisms of EASE, including theoretically driven mediators (i.e., anxiety sensitivity, subsequent changes in COVID-19 related stress and fear) and moderators (i.e., perceived racial discrimination, social support, and socioeconomic status).

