**Follow-up timeline:** Participants will complete follow-up assessments at 3- and 6-months following the baseline assessment, which will also be completed using the Insight app, in the same manner as the baseline assessment. Assessments to be conducted have been detailed below (please see 10.0 procedures involved). We expect the 3- and 6-month follow up assessment sessions will each take participants approximately 30 minutes to complete. Moreover, during the time between the baseline and 6-month follow-up assessments (6-month continuous assessment period) participants will continue to receive daily EMAs and will have access to all intervention materials included in the app.

**Project Timeline.** Year 1 will focus on obtaining IRB approval (i.e., submit application, respond to reviewers, and re-submit), hiring and training research staff, and beginning the enrollment. Year 2 will focus on recruitment, enrollment, and collecting follow-up data. Year 3 will focus on collecting follow-up data, data cleaning/analysis, and manuscript preparation and dissemination, including presenting findings at professional conferences and community-based events. For the present study, we expect approximately 50% of participants who click on our advertisement to be eligible; 75% of those who complete the phone screener to be eligible; and 95% of those to consent to participate. Weighted compensation schedule and reminder calls will be utilized to minimize subject dropout. Based on our ongoing work, we expect to enroll 39 participants each month, on average, across the 21-month enrollment period. We expect to retain 80-90% of subjects at each follow-up assessment points.

Project Timeline

ACTIVITIES TO BE COMPLETED	Year 1				Year 2				Year 3			
	Q1	Q2	Q3	Q4	Q1	Q2	Q3	Q4	Q1	Q2	Q3	Q4
HIRING AND TRAINING STAFF; STUDY PREPARATION	•											
IRB SUBMISSION AND APPROVAL	•											
ENROLLMENT AND ADMINISTER STUDY PROCEDURES		•	•	•	•	•	•	•	•	•		
DATA CLEANING									•	•		
DATA ANALYSIS & DISSEMINATION									•	•	•	•

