Q1: Months 1-3, Q2: Months 4-6, Q3: Months 7-9, Q4: Months 10-12. *Study Implementation (Year 1):* Staff hiring and training; IRB submission; and recruitment preparation. *Enrollment and Study Procedures (Years 1-3):* Recruitment; screening; enrollment; assessment; and follow-up. *Data Cleaning and Dissemination (Years 3):* Collect follow-up data; data cleaning and merging, analysis, and interpretation; research dissemination preparation; and manuscript preparation.

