
**Baseline assessment:**

During the baseline assessment, all participants will be asked to download the Insight app. Upon downloading Insight, participants will be provided with a unique activation code which they will enter onto Insight to gain access to the Baseline assessment. Upon completion of the Baseline assessment, the app will request a second code that will be used to place participants in the correct group.

Though participants will be assigned to different mobile interventions, all participants will use the Insight app to answer the baseline, follow-up, and EMA surveys. We will be using the Insight app to collect all of the study data (with the exception of the study screener, consent, and qualitative interviews which will be obtained via phone call and REDCap). Below is a detailed list of all study measures which will be administered to participants during their baseline session, via the Insight app:

Baseline measures:

Sociodemographic variables will be assessed using a standard form we have used in many prior studies. SES will be measured as income and education.

AS will be assessed using the 5-item SSASI we developed, which has excellent psychometric properties. Research has supported using a cut-off score of 5 to identify moderate to high AS

**FULL PROTOCOL TITLE:** Mobile Health to Monitor Risk for COVID-19 and Improve Mental Health during the Pandemic

individuals (reflecting top 1/3rd of distribution).

The Sheehan Disability Scale (SDS) is a psychometrically sound, brief, 5-item self-report tool that assesses functional impairment in work/school, social life, and family life.

The Social Support Questionnaire-Short Form (F-SozU K-6) List is a well-validated 6-item measure of social support.

The PEG scale is ultra-brief 3-item measure derived from the brief pain inventory and validated in ambulatory care settings. It demonstrates strong properties to detect change in pain.

The Everyday Discrimination Scale is a 6-item, validated measure of discrimination.

The Coronavirus Racial Bias Scale (CRBS) is a 4-item Likert scale designed to assess disparities in COVID-19, including likelihood of contracting COVID-19, lack of appropriate healthcare, as well as negative social medial posts against certain racial groups.

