Data analysis overview: Hypotheses for Aims 1 and 2 will be examined using latent growth models (LGM), multilevel structural equation models (MSEM) and latent difference score models using MPlus 8.0. To simplify subsequent sections, an overview of the common data analysis elements is presented first. Data will first be examined for multivariate normality and outliers to determine the most appropriate estimator. The maximum likelihood (ML) estimator will be used if data are approximately normal. Robust maximum likelihood (MLR) will be used if the data are not multivariate normal. We anticipate some participant attrition during the trial. Missing data will be handled in all analyses using direct ML techniques within MPlus under a missing at random (MAR) assumption. Modern missing data techniques such as direct ML increase statistical power and provide more accurate estimates of model parameters and standard errors and are the recommended intent-to-treat approach for clinical trials. LGM will generally be used to model outcomes collected at major assessments. MSEM will be used to further examine the longitudinal course of outcomes and hypothesized mechanisms of action as MSEM is ideally suited for disentangling within and between individual variance in order to more precisely estimate main effects, lagged effects, and indirect effects in intensive longitudinal designs. Evaluation of model fit in the LGM/MSEM models will be examined using fit diagnostics (i.e., standardized residuals) and common fit statistics (i.e., root mean square error of approximation) following the associated cutoff criteria recommended by Hu & Bentler. We will assess the equivalence of the treatment groups on key baseline

**FULL PROTOCOL TITLE:** Mobile Health to Monitor Risk for COVID-19 and Improve Mental Health during the Pandemic

variables (demographics and psychological variables); variables on which the groups differ will be used as covariates in the final analyses. We will also examine attrition from the study as a dichotomous outcome and use logistic regression to determine if treatment assignment predicts attrition.

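### Aim 1 gives 420 per arm (840) but Section 5.0 randomises 440 per arm (880, four groups of 220); the figures are neither reconciled nor labelled, and the accrual forecast does not say what is counted as enrolled

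*Combined protocol and SAP*

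**What the plan says.** Section 1.0, Aim 1, sets out the main comparison: "To compare the effect of EASE with COVID-19 specific elements (n = 420) to a standard-of-care digital intervention". The control description ends with the same number: "anxiety and depression symptom management and COVID-19 specific elements (n = 420". Neither figure carries a label such as randomised, retained or analysed.

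Section 5.0 (Number of Subjects) gives a different size: "We anticipate randomizing a total of 880 participants (N = 880; 220 Black, 220 Hispanic, 220 American Indian, and 220 NLW; Intervention group, n=440". The control arm is also 440. The same section expects 1300 people to consent, allowing for failed screeners and attrition.

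Section 3.0, exclusion criterion 4, turns a person away once the cell for their race/ethnicity is full. It gives no cell size.

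Section 8.0 (Project Timeline) gives the accrual forecast, "we expect to enroll 39 participants each month, on average, across the 21-month enrollment period", and the retention forecast, "We expect to retain 80-90% of subjects at each follow-up assessment points". It does not say whether enrolment is counted at consent or at randomisation.

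**The concern.** Two current sections give different sizes for the same two-arm comparison, and no visible text explains the difference. The sample size is a number that the trial recruits to. It also fixes the race/ethnic cells, and it bears on Aim 1's plan to examine efficacy within each group. Section 9.0 defines the primary study endpoint as completed recruitment of all subjects, so a reader needs to know which total completes it.

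The rest of the plan makes the randomised number the natural one for Aim 1. Section 20.0 handles missing data by direct maximum likelihood, methods of which it says that they "are the recommended intent-to-treat approach for clinical trials". Section 10.0 puts the baseline assessment before group placement: "Upon completion of the Baseline assessment, the app will request a second code that will be used to place participants in the correct group". Every randomised participant should therefore have baseline data for such an analysis. This is an expectation about what Aim 1 would show. It does not prove that 420 is wrong.

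The accrual forecast is a secondary matter: its product matches neither the randomised nor the consented number in Section 5.0.

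**Working it through.** **Inputs.** Section 1.0: 420 and 420. Section 5.0: 880 randomised, 440 per arm, four groups of 220, 1300 consented. Section 8.0: 39 per month, 21 months, 80-90% retention at each follow-up.

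**1. Does Section 5.0 add up?** 2 × 440 = 880 and 4 × 220 = 880. Yes.

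**2. Does Aim 1 agree with it?** 2 × 420 = 840. The difference is 880 − 840 = 40, or 20 per arm; 40/880 = 4.5%. It does not agree.

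**3. Which cell size can the exclusion rule mean?** The only one stated is 220. Four cells of 220 make 880, which exceeds 840 by 40. Equal cells under 840 would be 840/4 = 210, but that is a division made here; the documents give no such cell size.

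**4. Could 840 be what remains of 880 after attrition?**
- At a single follow-up: 880 × 0.80 = 704 and 880 × 0.90 = 792. Neither is 840.
- With at least one of the two follow-ups: this share is not stated. If 80% attend each, it lies between 80% (the same people both times) and 100% (nobody misses both). The ratio 840/880 = 95.5% lies inside that range.

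Attrition at one visit does not explain 840. A count of people with at least one follow-up could.

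**5. The accrual forecast.** 39 × 21 = 819.

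| If enrolment means | Section 5.0 number | Shortfall | Share | Months at 39 per month |
|---|---|---|---|---|
| Randomised | 880 | 880 − 819 = 61 | 61/880 = 6.9% | 880/39 = 22.6 |
| Consented | 1300 | 1300 − 819 = 481 | 481/1300 = 37% | 1300/39 = 33.3 |

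Against Aim 1's 840, the shortfall is 21 (21/840 = 2.5%). The 21 months do fit the timeline grid: the study-procedures row covers nine quarters, 27 months, and 27 − 6 months of follow-up = 21. The period is therefore not the source of the gap.

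**6. Effect on power.** The visible text gives no alpha, power, effect size or SD. Assume a two-sided alpha of 0.05, 80% power, a simple comparison of two means and no dropout. The detectable standardised difference is (1.960 + 0.842) × √(2/n):
- n = 420: 0.193
- n = 440: 0.189

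With 20% dropout the values are 0.216 and 0.211. The choice between the two sizes makes no practical difference to power.

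**The case against.** The best defence is that there is little doubt in practice. Section 5.0 is the dedicated section, its numbers agree with each other, and it alone says how many are randomised. The exclusion rule therefore has one available cell size, and 420 in Aim 1 may simply be a count of another kind. Most of this stands. It means that criterion 4 does not face two competing stated cell sizes. It does not remove the conflict, because Aim 1 still shows a different, unlabelled number for the same comparison.

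A reader might infer from the 80-90% retention forecast that 840 cannot be an attrition-adjusted count and must be a mistake. The documents do not support that, because a count with at least one follow-up could reach 95.5%.

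A reader might also infer that accrual will fall short or that the project will overrun. That goes too far as well. The 39 per month is an average forecast that Section 8.0 bases on the team's ongoing work, and the shortfall depends on a meaning of enrolment that the text does not fix. On the randomised reading, accrual runs 22.6 − 21 = 1.6 months longer, which is less than one three-month column of the timeline grid. Year 3 already combines late follow-up with closing work ("Collect follow-up data; data cleaning and merging, analysis, and interpretation"), and the project runs for three years.

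Finally, Section 22.0 (Resources) is not in the text available for review, so an explanation there cannot be excluded. Even so, Sections 1.0 and 5.0 would still differ as they stand.

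**Conclusion.** The inconsistency is real and minor. Aim 1 totals 840 and Section 5.0 totals 880, a difference of 40 people (4.5% of 880), and no visible section reconciles or labels the figures. Section 5.0 is internally consistent and is the only source of a randomised total and a cell size, and its four cells of 220 do not fit 840. The documents do not settle which total is intended.

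Secondarily, the forecast of 819 is 61 below 880 if enrolment means randomised and 481 below 1300 if it means consented, so the term needs a definition.

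It would be wrong to conclude that the trial is underpowered: the detectable difference moves only from 0.189 to 0.193 SD under the assumptions stated above. No feasibility problem is shown either. The point rests on the visible text alone and on simple arithmetic.

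**What to change.** 1. In Sections 1.0 and 5.0, state one randomised total with matching per-arm and per-cell numbers. If Section 5.0 is current, change Aim 1 to 440 per arm. If Aim 1 is current, correct the total, arms and cells in Section 5.0.
2. If 420 is not the randomised number, keep it but say in Aim 1 what it counts.
3. In Section 8.0, say whether enrolment means consented or randomised, and restate the expected duration to match. For 880 randomised at 39 per month this is about 22.6 months. The rate should not be raised merely to make the product fit, since that would replace a forecast based on ongoing work with one that has no stated evidence.

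A pointer from exclusion criterion 4 to the cell size would be convenient but is not essential.

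The cost is a few wording changes. If 880 is kept and enrolment means randomised, the stated accrual period lengthens by about 1.6 months, within the three-year project. No change to the analysis is needed.

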## **6.0 Recruitment Methods**

### **STUDY WIDE:**

Participants will be recruited online via social media and internet outlet (e.g. Craigslist, Facebook) advertisements that target residents of the United States. Individuals who click our ads will read the study description and complete a brief study screener in REDCap. We will also utilize university and online LISTSERV services to recruit participants, as well as Qualtrics Panels Recruitment to gather basic demographic information to assess primary eligibility. Also, we will be recruiting American Indian participants through BuildClinical. BuildClinical is a data-driven platform that helps academic researchers recruit participants for research studies more efficiently using social media, software, and machine learning. BuildClinical will direct individuals to their own platform where they will receive more information about the study. They will also be able to take our pre-screener survey through BuildClinical and we will be able to download a list of pre-eligible participants. This program will have access to the following information: (1) Full name, (2) Phone number, (3) Phone number (secondary), (4) Email address, (5) Age, (6) Date of birth, (7) Ethnicity, (8) Race, and (9) Gender assigned at birth. BuildClinical

**FULL PROTOCOL TITLE:** Mobile Health to Monitor Risk for COVID-19 and Improve Mental Health during the Pandemic

does not interact with data outside of sending the data to the University of Houston. BuildClinical's Secure Socket Layer (SSL) software encrypts all inputted information and keeps the information private and compliant. BuildClinical will create all recruitment materials for use on their platform once recruitment through BuildClinical is approved by the University of Houston Institutional Review Board. Those who initially meet the study inclusion criteria will complete a phone call with study staff after completing the REDCap screener. During this call, study staff will verify that individuals meet the study inclusion criteria and staff will review study details with each individual. We will also post flyers in the community and around the UH and OU campuses as permitted (flyer attached). Additionally, we will recruit residents specifically from OK and TX through various media outlets (e.g. TV, Radio). Finally, we will utilize community organizations (e.g. Legacy Health, Lone Star clinic) for recruitment purposes as well.

